#### Handling of Incomplete Dates

For **AE dates** or the relationship of an AE to the study drug, missing dates will be handled as follows:

**1) AE start date:**

- If the year and month are known and the month/year are earlier than the first study drug administration, the last day of the known month will be used.
- If the year and month are known and the month/year are the same as the first study drug administration, the AE start date will be the same as the date of the first study drug administration (i.e., "xx month xx day").
- If the year and month are known and the month/year are later than the first study drug administration, the first day of the known month will be used.
- If only the year is known and it is earlier than the year of first study drug administration, December 31 of that year will be used.
- If only the year is known and it is the same as the year of first study drug administration, the AE start date will be the date of the first study drug administration (i.e., "xx month xx day").
- If only the year is known and it is later than the year of first study drug administration, January 1 of that year will be used.
- If the year, month, and day are all missing, the date of the first study drug administration will be used as the AE start date.

**2) AE end date**

- If the year and month are known, the last day of the known month will be used.
- If only the year is known, December 31 of that year will be used.
- If the imputed start date is after the imputed end date, the end date will be adjusted to match the start date.
- In all other cases, the data will be treated as missing.

For **CM (concomitant medication) dates, missing data will be handled as follows:**

**1) Start date of CM:**

- If the year and month are known, the first day of the known month will be used.
- If only the year is known, January 1 of that year will be used.
- If the year, month, and day are all missing, no imputation will be performed for the start date.

**2) End date of CM:**

- If the year and month are known, the last day of the known month will be used.
- If only the year is known, December 31 of that year will be used.
- If the imputed end date is after the last study visit date, the last study visit date will be used as the end date.

- If the year, month, and day are all missing, no imputation will be performed for the end date.

If the relationship between an AE and the study drug is missing, the AE will be classified as drug-related for the purpose of summary reporting.

For all other missing data in this study, no imputation will be performed, and the data will be analyzed and described in their original state as collected.

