#### 3.2.2 Reporting standards for analysis results

The ITT, m-ITT, and PPS datasets will be analyzed according to the randomized treatment groups, while the AT and SS datasets will be analyzed based on the actual interventions received. Issues related to cases or data handling not explicitly described in the clinical trial protocol will be resolved following case discussions.

Continuous variables will be described using the mean, standard deviation, median, quartiles, minimum, and maximum values. Categorical and ordinal data will be summarized using frequencies and percentages. Statistical measures and the number of decimal places will be reported as outlined in the table below:

Name	Description	Decimal Places (dp)
Quantitative Data		
N	Number of subjects without missing results	0 dp
Mean	Arithmetic mean	Raw data decimal places + 1 dp

SD	Standard deviation	Raw data decimal places + 1 dp
Median	Median value	Raw data decimal places
Q1	25th percentile (first quartile)	Raw data decimal places
Q3	75th percentile (third quartile)	Raw data decimal places
Min	Minimum value	Raw data decimal places
Max	Maximum value	Raw data decimal places
Missing	Number of missing cases	0 dp; if the percentage frequency is less than 0.1%, the percentage will be displayed to the first non-zero digit. For example, if the percentage is "0.000523%", it will be displayed as "0.0005%" instead of "0.0%".
Qualitative (Categorical and Ordinal) data		
n	Number of subjects with a specific evaluation indicator value	0 dp
%	Percentage (0-100%)	1 dp
Statistical measures		
95% CI	95% confidence interval	Raw data decimal places + 2 dp

The comparison of baseline characteristics between the two groups will be conducted using appropriate statistical methods according to the type of data. For quantitative variables, an independent samples t-test will be used if normality and homogeneity of variance are satisfied; otherwise, the Wilcoxon rank-sum test will be applied. For categorical data, a chi-square test will be used if all expected cell counts are  $\geq 5$ , a continuity-corrected chi-square test will be used if one expected cell count is between 1 and 5, and Fisher's exact test will be applied if more than one expected cell count is between 1 and 5, or if any expected cell count is  $< 1$ . For ordinal data, the Wilcoxon rank-sum test will be used without adjusting for center effects, while the Cochran-Mantel-Haenszel (CMH) test will be applied if adjustments for center effects are needed.

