### 3.2.3 Rules for handling missing data

Any requested data that is not provided will be considered as missing data.

Missing data will be displayed as “ ” in the listings. If data is recorded as “Not Applicable” (NA) or “Not Known” (NK), such data will appear in the listings as per their original record. However, for statistical analysis, they will be treated as missing data.

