#### Handling of missing efficacy data

The primary efficacy analysis will be conducted based on the m-ITT population, and every subject must have a 90-day mRS score. If a subject dies before 90 days, they will not be considered missing and will be assigned the highest mRS score of 6 for evaluation. If the 90-day mRS value is missing but the subject's survival is confirmed within 90 days, the last available observation (e.g., from day 5 or discharge) will be carried forward to impute the missing value. For subjects with an unknown survival status at 90 days, the worst possible score (mRS = 6) will be assigned.

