#### 3.9.2 Secondary efficacy endpoints

The secondary efficacy endpoints are as following:

- (1) Proportions of patients with mRS = 0 or 1 at 90 days after stroke onset.
- (2) Proportions of patients with mRS = 0–3 at 90 days after stroke onset.
- (3) mRS score at 90 days after stroke onset.

(4) NIHSS score at 18–24 hours after procedure, 24–74 hours after procedure, and 5–7 days after stroke onset and their changes from baseline.

(5) Proportions of patients with a NIHSS score = 0 or 1, a NIHSS score = 0–2, a NIHSS score improvement  $\geq 4$  points, and a NIHSS score improvement  $\geq 8$  points at 18–24 hours after procedure, 24–74 hours after procedure, and 5–7 days after stroke onset.

(6) Glasgow coma scale score (GCS) at 18–24 hours after procedure, 24–74 hours after procedure, and 5–7 days after stroke onset and their changes from baseline.

(7) Barthel Index score (BI) and proportions of patients with BI = 95–100 at 30 and 90 days after stroke onset.

(8) EQ-5D-5L score at 90 days after stroke onset.

(9) eTICI score and successful reperfusion rates before and after EVT.

(10) mAOL score and recanalization rates at 24–72 hours after procedure.

(11) PC-ASPECTS score at 24–72 hours after procedure and 5–7 days after stroke onset.

(12) Lesion volume based on quantitative imaging detection at 24–72 hours after procedure and 5–7 days after stroke onset.

For categorical endpoints (1, 2, 5, 7, 9, and 10), proportions will be calculated with 95% CI using the exact Clopper-Pearson method. Group comparisons will use chi-square tests, continuity-corrected chi-square tests, or Fisher's exact test, as appropriate, and P-values will be reported. RD and RR with 95% CIs will also be calculated. Both unadjusted and adjusted results will be reported. Covariates include age, pre-stroke mRS, time from onset to randomization, NIHSS score, and collateral circulation.

For continuous endpoints (4, 6, 7, 8, 11, and 12), group comparisons will use independent samples t-tests (if normality and homogeneity of variance are satisfied) or Wilcoxon rank-sum tests (if not). Mean differences with 95% CIs will also be calculated. Both unadjusted and adjusted results will be reported. Covariates include age, pre-stroke mRS, time from onset to randomization, NIHSS score, and collateral circulation.

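### Only the 90-day mRS has a rule for death, so the continuous BI, EQ-5D-5L, NIHSS and GCS comparisons are made in survivors only, and the denominator for the NIHSS and BI proportions is not stated.

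*SAP*

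**What the plan says.** SAP 3.2.3 opens with a broad definition: "Any requested data that is not provided will be considered as missing data". Its part on missing efficacy data deals with the 90-day mRS only. For patients who die before day 90, "they will not be considered missing and will be assigned the highest mRS score of 6 for evaluation". Known survivors without a 90-day mRS have their last observation carried forward, and "For subjects with an unknown survival status at 90 days, the worst possible score (mRS = 6) will be assigned". After the rules for adverse-event and medication dates, the section closes with "For all other missing data in this study, no imputation will be performed", and such data are analysed as collected.

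In the reporting table of SAP 3.2.2, N for quantitative data is the "Number of subjects without missing results". The rows for qualitative data define a count and a percentage but no denominator.

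SAP 3.9.2 then says "For continuous endpoints (4, 6, 7, 8, 11, and 12), group comparisons will use independent samples t-tests", or Wilcoxon tests where the assumptions fail, with mean differences, unadjusted and adjusted. The list covers NIHSS (4), GCS (6), BI (7), EQ-5D-5L (8) and two imaging measures (11, 12). For the binary endpoints it says "For categorical endpoints (1, 2, 5, 7, 9, and 10), proportions will be calculated with 95% CI using the exact Clopper-Pearson method".

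Protocol 8.4 says only in general terms that statistical methods will deal with missing data. Neither document gives a worst score, a worst rank or a survivor estimand for any scale other than the mRS.

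**The concern.** Survival is an outcome that arises after randomization. A comparison confined to patients alive at the visit no longer compares the randomized groups, even though SAP 3.1.2 analyses patients as randomized. If one strategy keeps alive some patients who would otherwise have died, and those patients are severely disabled, they lower that arm's average BI or EQ-5D-5L, while the other arm's deaths cost it nothing. The arm that saves lives then looks worse on function.

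The plan is also uneven within a single visit. At day 90 a death counts as a failure for mRS 0-1 and mRS 0-3 and as the worst category in the shift analysis, but it leaves the BI and EQ-5D-5L means.

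**Working it through.** **Reading the rules together.** A score absent because of death is requested data not provided, so it is missing under 3.2.3. It is not a 90-day mRS, so no value is imputed. N counts only non-missing values. The t-test or Wilcoxon comparison therefore runs on observed values. Patients who died are out, as is any survivor without a measurement. For the binary endpoints the chain stops one step short, because no denominator is given.

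**The plan's own figure.** The point rests on no stated number, but the simulation below uses the planned 170 per arm, which reproduces from SAP 1.5:
- n = (1.960 + 0.842)² × (0.4203×0.5797 + 0.2614×0.7386) / (0.4203 − 0.2614)² = 7.849 × 0.4367 / 0.02525 ≈ 135.8, so 136 per group.
- 136 / 0.80 = 170.

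**Size of the bias.** The documents give no mortality by arm, so all inputs here are assumed. Let mE and mI be mortality with EVT alone and with IVT followed by EVT, and let IVT followed by EVT be the arm with fewer deaths (the labels could be swapped). Let c be the mean BI of patients who survive under either strategy, with no treatment effect in them, and e the mean BI of the additional survivors.
- Survivors only: difference = [(1 − mE)c + (mE − mI)e] / (1 − mI) − c = (mE − mI)(e − c) / (1 − mI).
- Death scored 0: difference = (mE − mI)e.

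The signs differ whenever mE > mI and 0 < e < c. Worked example at 35% versus 25%, c = 70, e = 20:
- Survivors: (0.65×70 + 0.10×20)/0.75 = 63.3 against 70, so −6.7.
- Death = 0: 47.5 against 45.5, so +2.0.

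| mE / mI | c | e | Survivors only | Death = 0 |
|---|---|---|---|---|
| 35% / 25% | 70 | 20 | −6.7 | +2.0 |
| 30% / 25% | 70 | 20 | −3.3 | +1.0 |
| 40% / 30% | 60 | 10 to 30 | −7.1 to −4.3 | +1.0 to +3.0 |
| 30% / 25% | 60 | 10 to 30 | −3.3 to −2.0 | +0.5 to +1.5 |
| 35% / 25% | 70 | 70 | 0 | +7.0 |
| equal | any | any | 0 | 0 |

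**Proportions.** At 35% versus 25%, suppose half of those who survive under either strategy reach BI 95-100 and no additional survivor does. Over all patients the proportion is 0.5 × 65% = 32.5% in both arms. If deaths are dropped, it is 32.5/75 = 43.3% against 32.5/65 = 50.0%, a difference of −6.7 points. If deaths are kept, it is 0. The unstated denominator decides which of these is reported.

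**Simulation.** 170 per arm, 1,500 trials per scenario, c = 60 with SD 30, e = 10 or 30, BI rounded to steps of 5 and limited to 0-100, and mortality of 30/25%, 40/30% or 25/15%. The survivor-only difference went against the arm with fewer deaths in 72% to 95% of trials, and did so with two-sided p < 0.05 in 9% to 34%. With 40% mortality in both arms, or with additional survivors no worse than the others (e = 60), the corresponding figures were 48% to 50% and about 2.5%, which is chance.

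**The case against.** The primary endpoint, mRS 0-1, mRS 0-3 and the mRS shift all score death, and SAP 3.10 reports mortality with Kaplan-Meier curves and a log-rank test. A reader would see functional results that include deaths beside any survivor-only BI mean. This stands, and it is why the point concerns secondary endpoints only. It does not correct the BI or EQ-5D-5L comparison itself.

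A reader might infer four stronger claims that the documents do not support:
- **That the SAP removes deaths from the NIHSS and BI proportions.** It does not say so. The N definition belongs to quantitative data, SAP 3.9 makes m-ITT the primary efficacy set, and counting deaths as failures over that set is not excluded. The table shells are in an attachment not available here.
- **That the SAP forbids all other imputation.** It also fills in mRS values for survivors and for patients of unknown status, adverse-event and medication dates, and event relationship. Only efficacy values other than the 90-day mRS are left without a rule.
- **That the results will point the wrong way.** Reversal needs unequal mortality and additional survivors who are worse off than the others. The protocol's Introduction cites three anterior-circulation randomized trials with no significant mortality difference, against a meta-analysis and a real-world study suggesting lower mortality with thrombolysis. Its remark on extreme mortality refers to untreated patients, whereas both arms here receive EVT.
- **That all scales are affected alike.** NIHSS and GCS end at days 5-7, when fewer deaths will have accrued than by day 90.

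**Conclusion.** The point holds for the continuous analyses: as written, BI, EQ-5D-5L, NIHSS and GCS are compared among survivors. For the NIHSS and BI proportions it is an omission, because the denominator is not stated.

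The consequence is conditional. If mortality differs and the additional survivors are more disabled than the rest, the bias runs against the arm with fewer deaths. On the assumed inputs it amounts to about 2 to 7 BI points, enough to reverse the sign. If mortality is equal there is no systematic reversal. If the additional survivors resemble the others, the survivor comparison is near zero rather than reversed, but it misses the gain from fewer deaths.

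The impact is greatest for BI at 30 and 90 days and EQ-5D-5L at 90 days. The primary conclusion is not affected. The change should be made before the final analysis, but the trial's main result does not depend on it.

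**What to change.** Add to SAP 3.2.3 and 3.9.2:
- (a) Patients who died before an assessment count as non-success in every NIHSS and BI proportion, with the m-ITT set as denominator.
- (b) For BI, EQ-5D-5L, NIHSS and GCS, including change from baseline, death is ranked worse than any observed value. The main comparison is rank-based: Wilcoxon, with an ordinal or rank model for the covariate-adjusted result. Ranking avoids having to choose a numeric EQ-5D value for death (no value set is named) or an NIHSS change score for a patient who died.
- (c) Survivor-only means and mean differences are kept and labelled descriptive.

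The cost is SAP wording and modest programming, with no new data. Wilcoxon tests and ordinal regression are already in SAP 3.9.2. Rank effects are less directly interpretable than mean differences. The change removes a bias but does not add much power: in the simulated scenarios with reversal, the comparison with deaths ranked worst was significant in favour of the arm with fewer deaths in only 5% to 18% of trials.

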4.3 Inclusion criteria

Participants must meet all of the following criteria to be eligible for enrollment:

- (1) A clinical diagnosis of AIS.

(2) Caused by BAO confirmed by CTA, MRA, or DSA. (BAO is defined as the absence of visualization of the basilar artery on CTA, MRA or DSA. Bilateral vertebral artery occlusions or occlusion of a unilateral vertebral artery that is the sole supplier of the basilar artery, even in the presence of patent basilar artery, will be considered de facto BAO.)

(3) CT or MRI ruling out intracranial hemorrhage,

(4) Eligible for IVT and EVT (within 4.5 hours of symptom onset). (Symptoms onset is defined as point in time the patient was last seen well [at baseline] if patients are unable to provide a reliable history or the point in time when symptoms have started if patients can provide a reliable history. Symptoms onset includes diplopia, midline ataxia, visual loss, sensory or motor deficits, and conscious disturbance. Isolated vertigo [not accompanied by dysarthria, motor weakness, sensory symptoms, double vision, depressed level of consciousness] is not considered onset of symptoms.)

(5) NIHSS score ≥ 6 .

(6) Age ≥ 18 years.

(7) Signed informed consent by the patient or legal representative.

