10.2 Statistical analysis

The primary endpoint of the study is the proportion of patients achieving mRS ≤ 2 at 90 \pm 14 days after stroke onset. The proportion of patients achieving the primary endpoint will be calculated for each group, along with the rate difference (RD) and its 95% confidence interval (CI). A log-binomial model with a log-link function will be used to adjust the rate difference for multiple covariates, including age, pre-stroke mRS, time from onset to randomization, stroke severity (baseline NIHSS), and collateral circulation status (baseline PC-CS). The adjusted RD and its 95% CI will be reported.

For the shift analysis of mRS scores, a logistic ordinal regression model will be applied to calculate the common odds ratio (cOR) and its corresponding 95% CI.

The primary analysis will follow the intention-to-treat (ITT) principle. The main analysis will be based on a modified ITT population (m-ITT), defined as patients who were randomized and received treatment. Analyses will be conducted according to the original randomization group. Other populations, such as the as-treated set (ATS) and per-protocol set (PPS), will be used for sensitivity analyses. Details of the specific analytical methods and

population definitions can be found in the Statistical Analysis Plan (SAP).

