Appendix 14. PC-CS

(Source: *Int J Stroke*. 2016 Oct;11(7):768-75.)

[figure not shown]

Artery	Scoring Criteria	Points
PCoA	Diameter \geq ipsilateral P1 segment	2 points (each side)
	Diameter < ipsilateral P1 segment (hypoplastic)	1 point (each side)
PICA	Patent artery visible on CTA	1 point (each side)
AICA	Patent artery visible on CTA	1 point (each side)
SCA	Patent artery visible on CTA	1 point (each side)

Notes: PCoA, posterior communicating artery; PICA, posterior inferior cerebellar artery; AICA, anterior inferior cerebellar artery; SCA, superior cerebellar artery.

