#### 3.9.1 Primary efficacy endpoint

The primary efficacy endpoint, "the proportion of patients with mRS  $\leq 2$  at 90 days after onset," will be statistically described by treatment group. The 95% confidence intervals (CIs) will be calculated using the exact Clopper-Pearson method. Additionally, a bar chart will be used to display the distribution of mRS scores.

When using a superiority hypothesis test, the specific statistical hypotheses are as follows:

Null hypothesis  $H_0: p_T - p_C \leq 0$

Alternative hypothesis  $H_1: p_T - p_C > 0$

$\alpha = 0.025$  (one side)

If the hypothesis is adjusted to a non-inferiority hypothesis after the interim analysis, the specific statistical hypotheses are as follows:

Null hypothesis  $H_0: p_T - p_C \leq -15\%$

Alternative hypothesis  $H_1: p_T - p_C > -15\%$

$\alpha = 0.025$  (one side)

Here,  $p_T$  represent the proportions of patients with mRS  $\leq 2$  in the IVT followed by EVT and EVT alone groups, respectively.

A log-binomial model will be used, assuming the primary endpoint follows a binomial distribution. A log-link function will be applied, with covariates including age, pre-stroke mRS, time from onset to randomization, stroke severity (NIHSS score), and collateral circulation. Adjusted and unadjusted risk difference (RD) and risk ratio (RR) with their 95% confidence intervals will be reported.

For superiority, if the lower bound of the 95% CI of the adjusted RD  $> 0$ , superiority is established.

For non-inferiority, if the lower bound of the 95% CI of the adjusted RD  $> -15\%$ , non-inferiority is established.

Additionally, Chi-square tests (expected cell count  $\geq 5$ ), continuity-corrected chi-square tests (1 expected cell count between 1 and 5), or Fisher's exact test ( $\geq 1$  expected cell count  $< 5$  or any expected cell count  $< 1$ ) will also be used for group comparisons, and P-values will be reported.

The mRS score used in the primary analysis will be based on centralized assessments. If centralized assessments are missing for certain subjects, local investigator assessments will be used by default. Sensitivity analyses will also use local assessments to evaluate the robustness of the results.

A list of all primary efficacy endpoint data for all visits (m-ITT, AT, PPS sets) will be provided.

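### The adjusted risk difference decides the trial, but the SAP gives no way to keep a patient with a missing baseline covariate in that model

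*SAP*

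**What the plan says.** **Decision rule (SAP 3.9.1).** A log-binomial model is fitted "with covariates including age, pre-stroke mRS, time from onset to randomization, stroke severity (NIHSS score), and collateral circulation". Both conclusions are read from its adjusted estimate. "For superiority, if the lower bound of the 95% CI of the adjusted RD" exceeds 0, superiority is declared. "For non-inferiority, if the lower bound of the 95% CI of the adjusted RD" exceeds -15%, non-inferiority is declared. The unadjusted risk difference and a chi-square or Fisher comparison are also reported, but neither enters the rule. The SAP does not name the collateral score; Protocol 10.2 names baseline PC-CS.

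**Missing data (SAP 3.2.3).** For the primary analysis on the m-ITT set, "every subject must have a 90-day mRS score". Death counts as mRS 6, a patient known to be alive has the last observation carried forward, and unknown survival counts as mRS 6. Rules follow for incomplete adverse-event and concomitant-medication dates and for a missing adverse-event relationship. The section then closes with "For all other missing data in this study, no imputation will be performed".

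**Source of PC-CS.** Patients qualify with occlusion "Caused by BAO confirmed by CTA, MRA, or DSA" (Protocol 4.3). In Protocol Appendix 14, the rows for the three cerebellar arteries (PICA, AICA, SCA) read "Patent artery visible on CTA", while the posterior communicating artery rows name no modality. Protocol 8.1.6 says that PC-CS may be determined from CTA, MRA or DSA.

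**The concern.** The SAP takes care that no m-ITT patient lacks an outcome, even scoring unknown survival as the worst value. It takes no such care with the covariates, although the estimate that decides the trial depends on them. A regression cannot use a record with an empty covariate. With imputation excluded and no alternative named, that record is left out.

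A patient whose outcome was imputed would then count towards the decision, while one with a fully observed outcome but no PC-CS would not. The adjusted and unadjusted risk differences would rest on different denominators, and the deciding analysis would not be on the m-ITT set that SAP 3.9 and Protocol 10.2 promise. If the gap is noticed only after unblinding, the choice of a remedy becomes a data-dependent choice in the primary test.

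**Working it through.** **Step 1: which covariates are exposed.** Age, pre-stroke mRS, time from onset and NIHSS are eligibility variables or close to them (Protocol 4.3 and 4.4), so they should seldom be missing. PC-CS is not needed for eligibility and requires several vessels to be read on both sides. It is scheduled at baseline for everyone (Protocol Appendix 17, SAP 1.8), but no rate of unscored patients is given. The rate below is therefore an assumption.

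**Step 2: reproduce the plan's figures.** Inputs from SAP 1.5: p1 = 0.4203, p2 = 0.2614, difference d = 0.1589, one-sided alpha 0.025 (z = 1.960), power 80% (z = 0.8416), margin 0.15, dropout 20%.

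- Superiority: n = (1.960 + 0.8416)² × [p1(1 − p1) + p2(1 − p2)] / d² = 7.849 × 0.4367 / 0.02525 = 135.8, so 136 per arm as stated.
- Dropout: 272 / 0.8 = 340, or 170 per arm, as stated.
- Non-inferiority at 170 per arm with 0.4203 in both: SE = √(2 × 0.4203 × 0.5797 / 170) = 0.05354. Power = Φ(0.15 / 0.05354 − 1.960) = Φ(0.842) = 80.0%, as stated.

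**Step 3: choose the base.** Under SAP 3.2.3 a patient without a 90-day assessment receives a value and stays in. The number before any covariate loss is therefore the 170 per arm enrolled (taking all as treated), not 136.

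**Step 4: apply the loss.** Let f be the share without a covariate, lost at random and equally in both arms, so that n = 170 × (1 − f).

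- Non-inferiority power = Φ(0.15 / √(2 × 0.4203 × 0.5797 / n) − 1.960).
- Superiority power, with pooled variance under the null (mean rate 0.34085) = Φ([d√n − 1.960 × √(2 × 0.34085 × 0.65915)] / √0.4367).

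| f | n per arm | Non-inferiority power | Superiority power |
|---|---|---|---|
| 0% | 170 | 80.0% | 87.4% |
| 5% | 161.5 | 78.0% | 85.7% |
| 10% | 153 | 75.7% | 83.8% |
| 20% | 136 | 70.7% | 79.3% |

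Example at f = 10%: non-inferiority SE = √(0.4873 / 153) = 0.05644, and Φ(2.658 − 1.960) = Φ(0.698) = 75.7%.

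The last superiority entry is 79.3% rather than 80% only because the pooled form is slightly stricter than the unpooled form that gives 136.

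**Step 5: read the result.** Superiority carries a 20% allowance, so it roughly holds its target up to a 20% loss. Non-inferiority uses all 170 per arm to reach 80%, so any loss takes it below target.

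**The case against.** Several stronger readings are tempting, and the documents do not support them.

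- **That patients imaged by MRA or DSA have no PC-CS by design.** A reader could infer this from Appendix 14. Protocol 8.1.6 allows all three modalities, Protocol 8.3 has baseline imaging of any permitted kind assess collaterals, and Appendix 14 has no unscorable category. What remains is a mismatch of wording, which makes unscored patients plausible but does not establish them.
- **That the loss biases the randomised comparison.** Screening imaging comes before randomisation (Protocol 8.2, Appendix 20) and is read by a committee blinded to allocation (8.1.6). Missingness that follows the imaging pathway is fixed before the arm is known. It costs precision and narrows the population, but does not by itself favour an arm.
- **That superiority power drops well below 80%.** This follows only if one starts from 136 per arm, which removes the outcome dropouts that SAP 3.2.3 keeps in and then removes covariate losses as well.
- **That the SAP prescribes a complete-case analysis.** It never says so; the omission follows from how regression is fitted once imputation is barred. The patients also remain in the descriptive proportions, the unadjusted risk difference and the chi-square or Fisher comparison.

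All four qualifications stand. They do not remove the gap: the adjusted estimate alone decides, and the one general rule on other missing data forbids the usual way of keeping such patients in. Protocol 8.4 expects missing data to be handled by statistical methods, but the SAP supplies none for covariates.

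**Conclusion.** The point holds as a gap in the primary analysis. Patients with an outcome but a missing covariate, in practice mainly an unscored PC-CS, would leave the analysis on which both decisions rest, so it would not be the full m-ITT set. The harm is to precision and representativeness; no bias between arms is shown.

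Its size depends on a missing rate that the documents do not give. For an assumed 5 to 20%, non-inferiority power lies between about 78 and 71% against a planned 80%, and superiority power between about 86 and 79% against about 87% with no loss. These figures assume random and equal loss from 170 per arm. They ignore any precision gained by adjustment and any dilution from imputed outcomes. If almost every patient is scored, the effect is negligible. The exposure matters most if the trial moves to non-inferiority, which has no reserve.

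**What to change.** Add an exception to SAP 3.2.3: baseline covariates missing in the adjusted models are filled by a prespecified rule that uses neither arm nor outcome, so that every m-ITT patient contributes to the adjusted risk difference. The overall median, or a missing category for PC-CS, would do; one should be chosen before unblinding. Keep the complete-case analysis as sensitivity, and report the number of patients with each covariate missing by arm.

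Align the cerebellar-artery rows of Protocol Appendix 14 with Protocol 8.1.6, so that readers know how to score PC-CS on each permitted modality.

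The cost is one SAP sentence and a wording change in an appendix, with slightly weaker adjustment for patients whose value was filled in. No new data are needed.
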